### **Purpose of the Study:**

This is a prospective, randomized vanguard trial of trauma patients admitted to the trauma surgery service at IMC who are deemed to be at high risk for venous thromboembolism (VTE). Once identified and enrolled, subjects will be randomized to receive bilateral lower extremity duplex ultrasound (DUS) surveillance (see Appendix A) versus no surveillance. We will compare the two groups with regard to deep vein thrombosis (DVT) and pulmonary embolism (PE) rates, both during the index hospitalization and at 90 days post-discharge. To our knowledge, this is the first prospective, randomized study of its kind to occur since the widespread use of low molecular weight heparins (LMWH) for VTE chemoprophylaxis in trauma patients. The results of this trial will help to assess the feasibility of performing a definitive (likely multi-institutional) trial in the

future.

### **Hypothesis/Research Questions:**

This study will determine the rate of VTE (DVT and PE) in high-risk trauma patients who have surveillance for lower extremity DVT versus those who do not have surveillance. It will also determine the rate of DVT propagation to the popliteal vein or higher by 14 days after discharge in high-risk trauma patients found to have isolated distal DVT.

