In debating the utility of DUS in patients receiving prophylaxis with LMWH, one must acknowledge the emerging evidence questioning the current standard of LWMH dosing. Fixed twice-daily enoxaparin dosing for all patients has been found to result in subtherapeutic anti-Xa levels and thus may not constitute adequate prophylaxis. Data exists suggesting that a one-size-fits-all approach is inferior to a weight-based regimen using enoxaparin for VTE prophylaxis in trauma patients. [10] [11] As illustrated by the conflicting and poor retrospective data cited above, more evidence and prospective data is needed regarding the impact of DUS surveillance in trauma patient outcomes.

When assessing which trauma patients might warrant DUS screening, a risk assessment tool must be applied. The most common risk factors identified in the literature include age, ISS, specific underlying conditions, spinal cord injury, long bone and pelvic fractures. [7] [8] [9] [10] Two validated VTE risk assessment tools exist for hospitalized patients, one by Caprini and one by Maynard and Stein. [12] [13] Neither of these scoring systems, however, have been validated in the trauma patient population.

The risk assessment profile (RAP) score, developed by Greenfield in 1997, [14] has been validated retrospectively in two analyses, and may be more applicable to assessing the trauma patient population. [13] [15]

At IMC, our trauma service has adopted an aggressive VTE prophylaxis protocol that involves risk-stratifying patients upon admission. Currently, only high-risk patients for VTE in whom enoxaparin is contraindicated undergo regularly scheduled bilateral lower extremity DUS as surveillance for DVT. We hypothesize that high-risk trauma patients, regardless of chemoprophylaxis, who undergo scheduled DUS surveillance for lower extremity DVT will have a lower rate of symptomatic DVT, DVT propagation, and symptomatic or fatal pulmonary embolism (PE) than those who do not have screening.

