**Methods/Procedures:**

This is a prospective, randomized study with outcomes determined by blinded event adjudication (PROBE). Patients will be screened upon admission to the hospital, and enrolled within 24 hours from admission. Subjects will then be randomized to either the surveillance arm or the no surveillance arm. Subjects enrolled in the surveillance arm will undergo bilateral DUS on post-injury days 1, 3, 7, and every 7 days thereafter until discharge from the hospital. Subjects in the no surveillance arm will have routine hospital care on the trauma service, with no DUS performed unless symptomatic for DVT. (See Appendix B) Trauma physicians and advanced practice clinicians (APCs) will perform daily history and physical examinations targeted at eliciting symptoms and signs of potential VTE in all subjects.

All subjects enrolled in both arms of the study will have appropriate VTE prophylaxis provided (enoxaparin 30mg SQ every 12 hours if BMI<30, enoxaparin 0.5mg/kg SQ every 12 hours if BMI>30) according to the current IMC trauma service guidelines. VTE chemoprophylaxis will be started upon admission, or when deemed clinically safe according to the trauma service protocols. If chemoprophylaxis is not begun right away (because of solid organ injury, traumatic brain injury, etc.), those subjects will receive mechanical prophylaxis according to the trauma service guidelines.

Asymptomatic DVT in the surveillance group will be determined on the day of the DUS, prior to hospital discharge. Symptomatic DVT and PE during hospitalization in both groups will be pursued using the Wells score as guidance for DVT diagnosis and using objective imaging as diagnostic confirmation. 90 day follow-up of all subjects will be performed by reviewing medical records in the Intermountain Healthcare computerized medical record to look for evidence of VTE. All outcomes will be adjudicated by a panel of independent physician adjudicators blinded as to whether the patients were randomized to surveillance or not.

All subjects diagnosed with acute proximal DVT or PE will be treated with therapeutic doses of anticoagulants while in the hospital and after discharge, as appropriate. Subjects who are diagnosed with isolated calf DVT while in the hospital will have a follow up DUS on day 14 after

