the initial diagnosis to check for thrombus propagation, per current ACCP guidelines. Patients in whom thrombus propagates to the proximal deep veins will receive therapeutic anticoagulation unless contraindicated, according to the usual standard of care. See Appendix B for a flow chart that depicts treatment decisions throughout the study.

In order to investigate our hypothesis, this study will compare outcome variables between the surveillance and the non-surveillance groups.

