**Data Collection:**

[figure not shown]
The following variables will be collected for all subjects in both arms of the study in a secure, computerized database (REDcap):

1. Patient demographics
2. Past medical/surgical/family/social history
3. Mechanism of injury
4. Injuries sustained and Injury Severity Score (ISS)
5. All items in the Caprini DVT risk assessment model (See Appendix C)—this information will be used for descriptive purposes and as a means of comparing the two study groups.
6. All items in the Risk Assessment Profile (RAP) for VTE (See Appendix D)—this information will be used for descriptive purposes and as a means of comparing the two study groups.
7. VTE pharmacoprophylaxis agent, dose, time from admission to first dose, interruptions in pharmacoprophylaxis and for what reason
8. Mechanical prophylaxis modality used
9. Asymptomatic DVT in surveillance group with location
10. Symptomatic DVT/PE with location during hospitalization and at 90 days
11. DVT propagation with location during hospitalization and at 14 days
12. Major and clinically relevant bleeding during hospitalization and at 90 days (see Appendix E).
13. All cause mortality during hospitalization and at 90 days

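### DVT propagation is counted to 14 days after discharge but its dedicated scan is timed from diagnosis, and the hypothesis compares it between arms although only one arm is scanned systematically

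*Combined protocol and SAP*

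**What the plan says.** Hypothesis/Research Questions sets two aims. The second is to determine the "rate of DVT propagation to the popliteal vein or higher by 14 days after discharge", and it is limited to propagation "in high-risk trauma patients found to have isolated distal DVT". The window is tied to discharge, and the denominator depends on a distal clot having been found.

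Methods/Procedures provides one dedicated scan for this outcome. A patient whose isolated calf clot is found in hospital is rescanned once, 14 days on, counted from "the initial diagnosis to check for thrombus propagation". Its anchor is diagnosis. Data Collection, item 11, records "DVT propagation with location during hospitalization and at 14 days" and does not say what the 14 days are counted from. For the period after discharge, the other follow-up described is that "90 day follow-up of all subjects will be performed by reviewing medical records in the Intermountain Healthcare computerized medical record".

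The last paragraph of Background and Significance hypothesizes that screened patients "will have a lower rate of symptomatic DVT, DVT propagation" and symptomatic or fatal PE than unscreened patients. Methods/Procedures adds: "In order to investigate our hypothesis, this study will compare outcome variables between the surveillance and the non-surveillance groups". Propagation is not exempted. The same section gives the surveillance arm bilateral ultrasound on post-injury days 1, 3 and 7 and then weekly to discharge. The other arm is scanned only for symptoms.

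**The concern.** There are two separate difficulties.

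The first is the time window. A rate described as running to 14 days after discharge implies that patients are observed to that point. If the scan is timed from diagnosis, silent extension later in the window goes unseen unless someone happens to image for it. Because Data Collection leaves its 14 days unanchored, two analysts could report different propagation rates from the same records.

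The second is the contrast. A distal clot that is never imaged cannot be recorded as having propagated. If it extends and causes symptoms, it enters the record as a new proximal DVT. One arm is scanned serially and the other is not, so the number of distal clots available to propagate depends on the allocated strategy itself. A difference in recorded propagation could then reflect scanning and not the course of the disease. Blinded adjudication does not help, because adjudicators can only judge clots that were imaged. The trial is meant to inform a larger one, so an outcome that cannot be interpreted between arms should not be carried forward as part of its hypothesis.

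**Working it through.** No stated figure is in dispute. The check sets the sections side by side, with a little arithmetic.

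**1. Window.** Let d be the day of diagnosis and D the day of discharge. The dedicated scan applies to calf DVT diagnosed in hospital, so d ≤ D. The scan is on d + 14 and the window closes on D + 14.

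- Since d ≤ D, the scan is never later than the close of the window.
- If D − d ≤ 14, the stretch with no scheduled scan is (D + 14) − (d + 14) = D − d days, between 0 and 14. For example, with diagnosis on day 7 and discharge on day 12, the scan is on day 21, the window closes on day 26, and 5 days are unscanned.
- If D − d > 14, the day-14 scan happens before discharge. The text schedules nothing after discharge, so at least 14 days are unscanned.
- The scan and the end of the window coincide only when diagnosis falls on the day of discharge.

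This uses the text only. The Appendix B flow chart is not shown and could not be checked for another scan.

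**2. Contrast.** There are two ways to form a between-arm comparison.

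- *Per detected distal clot*, the denominator in the research question. The surveillance arm contributes silent and symptomatic clots; the other arm contributes mainly clots that caused symptoms. These are differently selected groups formed after randomization. Nothing in the documents says whether symptomatic distal clots propagate more or less often than silent ones, so no direction can be given.
- *Per randomized patient*. If propagation requires an earlier imaged distal clot and true risk is equal, the arm with more detected distal clots records more propagation. That is the surveillance arm, so the push is against the stated hypothesis.

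**3. Could the second effect be large?** Significance says about 85% of the DVTs diagnosed at the site are clinically silent. Let s be the silent share of clots detected under surveillance. If silent clots are never found in the other arm, the ratio of recorded propagation with equal true risk is 1/(1 − s):

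| s | ratio |
|---|---|
| 0.70 (assumed) | 1/0.30 = 3.3 |
| 0.85 (site figure, all DVT) | 1/0.15 = 6.7 |
| 0.90 (assumed) | 1/0.10 = 10.0 |

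This is an illustration, not an estimate. The 85% covers all DVT, not distal DVT. It also comes from current practice, in which only high-risk patients who cannot have enoxaparin are routinely scanned.

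**4. Number of events.** Data Analysis/Statistics expects about 300 patients per arm. The documents give neither the distal DVT rate under full scanning nor the propagation risk. Assuming 3% to 10% for the first and 10% to 20% for the second, recorded propagations with surveillance would number 300 × 0.03 × 0.10 = 0.9 to 300 × 0.10 × 0.20 = 6.0. Whatever the exact values, the count is likely to be small.

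**The case against.** The strongest reply is that little is at stake. The scan always falls within the stated window, so the discharge wording can be read as an outer bound and the day-14 scan as the way it is measured. The unanchored 14 days in Data Collection most naturally mean that scan. The formal research question asks for one descriptive rate. Purpose of the Study compares DVT and PE rates, and Data Analysis/Statistics names a test for VTE only. The contrast on propagation rests on one sentence in Background and Significance and a general sentence in Methods/Procedures.

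Most of this stands, and it sets the weight of the point. It does not remove the point. An outer bound that extends past the last scheduled look still yields a rate over a period not fully observed, and the hypothesis does name propagation as an outcome expected to be lower with surveillance.

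Three stronger readings are tempting, and the documents do not support them:

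- *That the scan misses the outcome window.* It does not; diagnosis cannot follow discharge for these patients.
- *That the contrast is certainly biased against surveillance.* This holds only per randomized patient, and only if an earlier imaged distal clot is required. The hypothesis gives no denominator. If it means any progression to a proximal vein, a symptomatic proximal DVT in the unscanned arm would count and the direction no longer follows.
- *That the bias is about 6.7-fold.* That figure applies a share of all DVT diagnosed under a different scanning practice to distal clots in arms it does not describe. Likewise, the site's 3% DVT rate is service-wide and cannot be used as the expected rate in a fully scanned high-risk arm.

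**Conclusion.** Both parts hold, at low severity.

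The propagation window runs past the last scheduled scan: by 0 to 14 days when discharge is within 14 days of diagnosis, and by at least 14 days when it is later. This follows from the text with no assumed dates, subject to the flow chart that could not be seen.

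Propagation as defined is not comparable between arms. On the protocol's own denominator the direction of the distortion is unknown. Per randomized patient, with an earlier imaged distal clot required and equal true risk, surveillance would show more propagation through detection alone. How much more cannot be derived from the documents; the 85% figure suggests only that it could be several-fold.

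The consequence is confined to how this outcome is interpreted. It does not touch the sample-size table, and no planned test depends on it.

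**What to change.** 1. In Hypothesis/Research Questions and in Data Collection item 11, define propagation as extension to the popliteal vein or higher seen by the scan on day 14 after initial diagnosis. List any propagation found later in the hospital stay separately, so that events on subsequent weekly scans are kept and not lost to the shorter window.
2. Remove propagation from the between-arm hypothesis in Background and Significance, and state in Methods/Procedures that it is not compared between arms. Symptomatic DVT and symptomatic or fatal PE stay as that hypothesis's outcomes.
3. Report propagation descriptively among patients with detected isolated distal DVT, by arm, with exact 95% confidence intervals and no test.

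**Cost.** Wording in four sections, with no new scan or data item. Purpose of the Study and Data Analysis/Statistics can stay as they are. The window becomes shorter than the one now stated, and the trial makes no between-arm claim on propagation. The intervals will be wide: by Clopper-Pearson, 1 of 5 gives 0.5% to 71.6%, 1 of 7 gives 0.4% to 57.9%, and 5 of 24 gives 7.1% to 42.2%. If the sponsor prefers the discharge anchor, an added or rescheduled outpatient scan would be needed.

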### **Background and Significance:**

Venous thromboembolism (VTE), comprised of DVT and PE, is a common complication of hospitalized patients. VTE affects an estimated 900,000 people in the U.S annually, and leads to about 300,000 deaths. [1] Major trauma patients are at an exceptionally high risk for developing DVT and PE. Without chemoprophylaxis, DVT incidence in trauma patients is as high as 58% in the lower extremities, with 18% of those being proximal [2]. Despite advances in VTE chemoprophylaxis and treatment with LMWH and methods of detection, VTE remains a significant source of morbidity and mortality in the trauma population.

Current guidelines recommend against routine screening for DVT with DUS in major trauma patients. [4] The evidence supporting this guideline, however, is not strong and continues to be sorely debated. Assessing a four-year prophylaxis and screening protocol, Adams et al. found that 86% of DVTs found on DUS are clinically silent, justifying the importance of routine surveillance in high-risk trauma patients. Additionally, they found that only 21% of VTE patients received enoxaparin within 48 hours of admission, illustrating the high incidence of delayed time to adequate chemoprophylaxis and the importance of this timing on risk assessment. [5] Napolitano et al. also identified four risk factors that place trauma patients at an increased risk of silent DVTs and propagation to PE, and suggested regular DUS in these patients. [6] Another approach was taken by Malhotra et al., who studied the cost-effectiveness of a DVT surveillance program in critically injured trauma patients. With a protocol of twice weekly DUS screening, they found a higher rate of DVT, a lower rate of PE, and concluded that their protocol was cost-effective based on quality adjusted life years saved. [7] On the contrary, Cipolle and colleagues found that despite decreasing DUS screening in major trauma patients, rate of PE was unchanged, concluding that strict adherence to a prophylaxis regimen was more important than surveillance. [8] They did recommend, however, regular DUS scans in patients they identified as high-risk, and when there was a delay to enoxaparin administration of greater than 48 hours. Schwarcz assessed the value of DUS surveillance in high-risk trauma patients and concluded that, in the setting of adequate chemoprophylaxis with enoxaparin, its utility is limited. [9]

In debating the utility of DUS in patients receiving prophylaxis with LMWH, one must acknowledge the emerging evidence questioning the current standard of LWMH dosing. Fixed twice-daily enoxaparin dosing for all patients has been found to result in subtherapeutic anti-Xa levels and thus may not constitute adequate prophylaxis. Data exists suggesting that a one-size-fits-all approach is inferior to a weight-based regimen using enoxaparin for VTE prophylaxis in trauma patients. [10] [11] As illustrated by the conflicting and poor retrospective data cited above, more evidence and prospective data is needed regarding the impact of DUS surveillance in trauma patient outcomes.

When assessing which trauma patients might warrant DUS screening, a risk assessment tool must be applied. The most common risk factors identified in the literature include age, ISS, specific underlying conditions, spinal cord injury, long bone and pelvic fractures. [7] [8] [9] [10] Two validated VTE risk assessment tools exist for hospitalized patients, one by Caprini and one by Maynard and Stein. [12] [13] Neither of these scoring systems, however, have been validated in the trauma patient population.

The risk assessment profile (RAP) score, developed by Greenfield in 1997, [14] has been validated retrospectively in two analyses, and may be more applicable to assessing the trauma patient population. [13] [15]

At IMC, our trauma service has adopted an aggressive VTE prophylaxis protocol that involves risk-stratifying patients upon admission. Currently, only high-risk patients for VTE in whom enoxaparin is contraindicated undergo regularly scheduled bilateral lower extremity DUS as surveillance for DVT. We hypothesize that high-risk trauma patients, regardless of chemoprophylaxis, who undergo scheduled DUS surveillance for lower extremity DVT will have a lower rate of symptomatic DVT, DVT propagation, and symptomatic or fatal pulmonary embolism (PE) than those who do not have screening.

### **Significance:**

VTE has been deemed a major threat by the US Surgeon General and the Centers for Medicare and Medicaid Services (CMS). Hospitals are under pressure to reduce or even eliminate VTE, or risk financial repercussions. The current ACCP guidelines do not differentiate high-risk trauma patients from lower-risk patients in the recommendations against routine DUS screening. Haut et al. identified significant variability in opinion and protocols among trauma surgeons and hospitals regarding regular screening for DVT, and found that the VTE rate may be more a function of surveillance bias than of the quality of care. [3] At our trauma service at IMC, our DVT rate is currently about 3%, [16] which has been deemed “too high” according to Intermountain

Healthcare and national targets. Most (approximately 85%) of the DVTs that we diagnose are clinically silent and are found during DUS surveillance of high risk patients.

If we were to discontinue routine DUS surveillance of the highest risk trauma patients, our DVT rate would certainly decrease. It is not at all clear, however, that this would translate to better overall patient outcomes, e.g., less PE, less major bleeding episodes, less mortality. It is very important to answer this question in a prospective, randomized fashion, as this has never been done since the advent of LMWH use for chemoprophylaxis.

**Recruitment:**

Subjects will be recruited from the trauma surgery service at IMC. This project involves direct patient contact and the collection of protected health information (PHI). The measures to protect PHI include:

1. The original subject data files and study data collection forms will be kept in a secure, locked cabinet in the Shock Trauma ICU at IMC, accessible only by study personnel. Electronic data files will be stored on a password-protected Intermountain Healthcare computer in a locked office.
2. Each subject in the research study will be assigned a unique identification number.
3. There will be no third party disclosure of patient identifying information.

**Research Subjects:**

Inclusion Criteria:

1. Inpatient status on IMC trauma surgery service, admitted within 24 hours of injury.
2. Age  $\geq 18$  at the time of injury
3. Meets the definition of high-risk for VTE according to current IMC trauma service guidelines (see Appendix A)

Exclusion Criteria:

1. Patient age  $< 18$  years at the time of admission to the hospital
2. Pregnancy
3. Prisoners
4. Patients with a life expectancy of less than 30 days
5. Patients with a known hypercoagulable state including:
  - a. Factor V Leiden
  - b. Protein C and S deficiencies
  - c. Dysfibrinogenemia of any sort
  - d. Active cancer

- e. Antiphospholipid antibody syndrome
- f. History of DVT or PE within past 6 months
- g. Myeloproliferative disorders
6. Patients on therapeutic anticoagulation who do not have their agent held upon admission to the hospital.
7. Patient elects to opt-out of the study

